## PROTOCOL SYNOPSIS Bose-ADHD POC-001

Study Product	Bose QC Noise Cancelling Headphones/Earbuds			
Protocol Number	Bose –ADHD POC-001			
Protocol Title	A randomized, sham-controlled, crossover study to evaluate the effects of noise cancelling headphones on neurocognitive and academic outcomes in children and adolescents diagnosed with Attention Deficit Hyperactivity Disorder (ADHD)			
Sponsor	Bose			
Study Phase	Pilot/Proof of Concept			
Study Start Date	Q1 2017			
Study Centers	Number of Centers = 1 (Duke University, PI [name])			
Hypothesis	Children with ADHD will demonstrate better performance on neurocognitive and academic outcomes in the presence of auditory distractors while using Bose noise cancelling headphones compared to performance when using a sham device.			
Primary Objective	Evaluate performance on the ADHD Battery of the Cambridge Automated Neuropsychological Test Battery (CANTAB), including spatial working memory, inhibitory control, and attention while using either a noise cancelling headphone or sham headphone control in the presence of standardized auditory distractors.			
	
 
Compare change from Baseline scores on the CANTAB ADHD battery with noise cancelling headphones and sham-controls.
 
			
Secondary Objectives	Evaluate performance on academic productivity measures (math and reading comprehension) while using either a noise cancelling headphone or a sham headphone control in the presence of standardized auditory distractors.			
	
 
Compare change from Baseline scores on academic productivity measures with noise cancelling headphones and sham-controls.
 
			
	Evaluate subjective reports of experience using the noise cancelling headphones and sham-controls during the assessment tasks.			
_	Compare the self-reports of noise cancelling headphones versus sham controls.  Evaluate Safety			
	Evaluate any differences in self-reported adverse effects from using the noise cancelling headphones or sham controls.			
Study Design	Overview			
	This will be a proof-of-concept, randomized, within-subject cross-over design with the administration of noise cancelling headphones or sham headphones on two separate study days. Following screening and a baseline assessment session with no headphones, participants will be assigned to complete each experimental session. During each session, they will undergo the CANTAB and Academic tasks. The order of sessions will be randomized and balanced across participants to be either noise-cancelling headphones first followed by sham headphones; or sham headphones first followed by noise-cancelling headphones.			

#### Inclusion/Exclusion Criteria

- Age 6 to 18 at the time of parental informed consent.
- Male or female.
- Confirmed ADHD diagnosis at screening/baseline visit established via MINI-KID administered by a trained clinician.
- Screening ADHD-RS-IV score ≥24.
- Estimated IQ (measured with the KBIT-2) ≥80.
- If currently medicated with a stimulant medication (amphetamine or methylphenidate formulation), off drug for a period of at least 48 hours prior to Baseline and Experimental Sessions.
- Able to follow written and verbal instructions (English) as assessed by the PI and/or study coordinator.
- Able to comply with all testing and requirements.

#### Exclusion

- Current controlled (requiring a restricted medication) or uncontrolled, comorbid psychiatric diagnosis, based on MINI-KID and subsequent clinical interviewing, with significant symptoms including but not limited to post-traumatic stress disorder, psychosis, bipolar illness, pervasive developmental disorder, severe obsessive-compulsive disorder, severe depressive or anxiety disorder, conduct disorder, or other symptomatic manifestations that in the opinion of the Investigator may confound study data/assessments (Participants with clinical history of learning disorders will be allowed to participate as long as the disorder does not impact their ability to participate based on PI judgement).
- Current treatment with any non-stimulant medication for ADHD (e.g., atomoxetine, clonidine, guanfacine).
- Current treatment with other psychoactive drugs.
- Participant is currently considered at risk for attempting suicide by the

Investigator, or is currently demonstrating active suicidal ideation or self-injurious behavior, as measured by MINI-KID Suicidality Module C.

- Documented hearing loss.
- Recent history or suspicion (within the past 6 months) of substance abuse or dependence.

Any other medical condition that, in the opinion of the Investigator, may confound study data/assessments.

#### Study Protocol

#### Recruitment & Randomization

30 children ages 6 to 18 will be recruited to participate.

Following a baseline assessment, participants will be randomized to receive 2 different sequences of experimental sessions (Noise cancellation headphones, then sham headphones; or sham headphones, then noise cancellation headphones). All participants will have a clinical diagnosis of ADHD and be willing to washout of any approved medication for 48 hours prior to the baseline and each experimental session.

#### Screening (Visit 1) Procedures

- Parental informed consent and participant assent will be obtained and demographic/contact.
- MINI-KID to confirm ADHD and assess presence of any other exclusionary psychopathology; and any suicidal ideation or behavior.
- Clinician-completed ADHD-RS to assess frequency/severity of ADHD symptoms.
- KBIT-2 to assess estimated IQ/intellectual functioning.
- Medical and developmental history, including current and past treatment.
- Participants who meet all inclusion and no exclusion criteria following screening will be scheduled for a baseline visit within 21 days of screening.

#### Baseline (Visit 2)

- Participants and their parents/caregivers will be assessed for any adverse events or changes in medical status since the last visit.
- Participants will complete the CANTAB ADHD battery with no headphones with standardized auditory distractors present. The CANTAB ADHD battery consists of the following subtests: Spatial Working Memory (SWM), Rapid Visual Information Processing (RVIP), and Stop Signal Task (SST).
- Participants will complete the Academic Productivity tasks for both math and reading comprehension with no headphones with standardized auditory distractors present.
- Participants will be fitted for the proper earbud size for headphones and practice inserting the earbuds.
- Participants will be randomized to one of the two experimental sequences and scheduled for Visit 3, to occur 7±3 days following the baseline visit.

#### Experimental Sessions (Visits 3-4)

- Participants and their parents/caregivers will be assessed for any adverse events or changes in medical status since the last visit.
- Participants will complete the CANTAB ADHD battery with either noise cancelling headphones or sham headphones control (depending on randomized sequence) with standardized auditory distractors present. The CANTAB ADHD battery consists of the following subtests: Spatial Working Memory (SWM), Rapid Visual Information Processing (RVIP), and Stop Signal Task (SST).
- Participants will complete the Academic Productivity tasks for both math and reading comprehension with either noise cancelling headphones or sham headphone control (depending on randomized sequence) with standardized auditory distractors present.
- Depending on which randomization sequence to which participants are assigned, either the noise cancellation or sham control earbuds will be used

# Analysis/Power Considerations

This study is designed as a proof-of-concept determination of the effects of noise cancelling headphones vs. sham headphone control on neurocognitive and academic outcomes.

#### Power

The current study is powered to detect a "moderate" yet clinically relevant effect size estimate of 0.50. Sample size calculations assumed a 2-tailed statistical test of size  $\alpha=0.05$ , power  $1\text{-}\beta=0.90$ , approximate normality of the test statistic, no period effect, equal carryover effects between the two sequences, a correlation between groups of 0.60, and equal variances between groups. Under these assumptions, a sample size of 28 will allow us to detect a "moderate" standardized effect size of 0.50 between the noise cancelling headphone condition and the sham headphone condition on the primary scalar outcome of interest.

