#### Data Analysis

Data will be analyzed using SAS software, version 9.4 (SAS Institute Inc., Cary, NC, USA). Data will be tested for normality using the Kolmogorov-Smirnov 'Goodness of Fit Test.' For normally distributed data, *t*-tests will be used to compare outcomes between noise cancelling headphones and sham headphone controls; for data that are not normally distributed, Wilcoxon's test will be used. We will also investigate for the effects of sequence on the outcomes. This will be accomplished using analysis of variance (RMANOVA) with a within factor of 'noise cancelling headphones on first study visit' vs. 'noise cancelling headphones on second study visit.' Because of the use of multiple tests on the same set of data, alpha adjustment will be conducted in accordance with the Bonferroni-Holm procedure. We will also calculate Cohen's d values for all outcomes as an estimate for relevant effect size estimates for future studies. Missing data will be managed using standard multiple imputation procedures.

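### Under the protocol's own assumptions, 28 children give about 81–84% power, not 90%, and the 30 to be recruited also fall short

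*Combined protocol and SAP*

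**What the plan says.** The only justification of the sample size is the paragraph headed Power, under Analysis/Power Considerations in the combined protocol and SAP. Its inputs are:

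- on sidedness, "Sample size calculations assumed a 2-tailed statistical test of size", where the value given for α is 0.05 and the target for power is 0.90;
- on the distribution, "approximate normality of the test statistic";
- on period and carryover, "no period effect, equal carryover effects between the two sequences";
- on the variance structure, "a correlation between groups of 0.60, and equal variances between groups".

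The conclusion begins "Under these assumptions, a sample size of 28 will allow us to detect a", and the effect in question, which the protocol calls moderate, is a "standardized effect size of 0.50 between the noise cancelling headphone condition and the sham headphone condition".

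Under Recruitment & Randomization, the target is slightly higher: "30 children ages 6 to 18 will be recruited to participate". No dropout rate is given, and nothing explains the step from 28 to 30. The Data Analysis section plans t-tests where outcomes are normally distributed and Wilcoxon's test otherwise, with a Bonferroni-Holm adjustment.

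**The concern.** The paragraph supplies every input needed to recompute the sample size, and the result is not 28. If the shortfall is real, the protocol claims a property that the design lacks: its chance of missing a true effect of 0.50 is larger than the stated 10%.

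That matters most if the trial finds no difference. A reader who trusts the 90% figure would take a null result as stronger evidence against the device than it is. The protocol also intends its effect sizes to inform future studies, so a misstated calculation could be carried into their planning.

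**Working it through.** **Inputs, all from the Power section.** Two-sided α = 0.05; power 0.90; effect d = 0.50 in units of the common SD of a condition; correlation ρ = 0.60; equal variances. No period effect and equal carryover reduce the two-period crossover to a paired comparison within child. The primary objective is worded as change from baseline, but there is a single baseline visit before the two sessions, so it cancels from the within-child contrast.

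**Step 1: paired effect.**
SD of the difference = √(2 × (1 − 0.60)) = √0.80 = 0.894.
Paired effect = 0.50 / 0.894 = 0.559.

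**Step 2: required n.**
n = (z for α/2 + z for power)² × 2(1 − ρ) / d² = (1.960 + 1.282)² × 0.80 / 0.25 = 10.507 × 3.2 = 33.6, so 34 by the normal approximation. With the noncentral t distribution, power is 89.5% at 35 and 90.3% at 36, so 36 are needed. The plan's 28 is not reproduced; the gap is 6 to 8 children.

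**Step 3: power at the stated and planned sizes.** By the normal approximation, power = Φ(0.559 × √n − 1.960). At 28 this is Φ(2.958 − 1.960) = Φ(0.998) = 84.1%.

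| Completers | Normal | Paired t (n − 1 df) | Crossover t (n − 2 df) |
|---|---|---|---|
| 28 | 84.1% | 81.4% | 81.3% |
| 30 | 86.5% | 84.1% | 84.0% |
| 34 | 90.3% | 88.6% | 88.5% |
| 36 | 91.8% | 90.3% | 90.3% |

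Type II error at 28 is 100 − 84.1 = 15.9% or 100 − 81.4 = 18.6%, that is, 1.6 to 1.9 times the stated 10%.

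**Step 4: what 28 would support at 90% power.**
- Detectable effect: 3.242 × 0.894 / √28 = 0.548 (normal), or 0.569 (t).
- Correlation needed to keep d = 0.50: 2(1 − ρ) = 28 × 0.25 / 10.507 = 0.666, so ρ = 0.667 (normal), or 0.691 (t).

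**Step 5: does another reading give 28?**

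| Reading | n, normal | n, t |
|---|---|---|
| As stated | 33.6 → 34 | 36 |
| One-sided 0.05, power 0.90 | 8.564 × 3.2 = 27.4 → 28 | 29 |
| Two-sided 0.05, power 0.80 | 25.1 → 26 | 28 |
| Two-sided 0.05, power 0.85 | 28.7 → 29 | 31 |
| 0.50 taken as the effect in SDs of the difference | 42.03 → 43 | 44 |
| Variance factor 1 − ρ² in place of 2(1 − ρ) | 26.9 → 27 | 29 |

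The two rows that give exactly 28 each contradict a stated input. Taking 0.50 on the difference scale widens the gap (power at 28 about 72% by t) and leaves the stated correlation with no role. Reading 28 as the number per sequence means 56 children, with 98–99% power, which conflicts with recruiting 30.

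**The case against.** The arithmetic is hard to contest, so the case on the other side concerns weight and framing.

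- *The protocol assumes approximate normality, so the fair figure is 84%, not 81%.* This is right as a like-for-like check, and even that most favourable basis misses 90%. Because the planned analysis is a t-test, the t-based figures are also legitimate. A corrected statement should name its basis.
- *Recruitment is 30, so the real gap is smaller.* This is true if every child completes: the shortfall is then 3.5 points (normal) or 5.9 points (t). But the protocol attaches its claim to 28.
- *This is a pilot, with no go/no-go rule tied to 90% power.* This limits the consequences. Type I error, the estimand and participant safety are unaffected, and how readers would treat a null result is a judgement. It does not make the figure correct: the protocol chose to claim a specific power.
- *The origin of 28 is unknown.* This stands. A one-sided test, 80% power, or a factor of 1 − ρ² (27, made even for balanced sequences) could each lead there. The last is not the variance of a paired difference under the stated assumptions. The inconsistency does not depend on knowing the source.

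**Conclusion.** The concern holds. Under the stated inputs, 90% power needs 34 completers (normal) or 36 (t). The stated 28 give 84.1% or 81.4%, and the planned 30 give 86.5% or 84.1% even with no losses. The difference is well beyond rounding.

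The result rests on reading 0.50 as the difference divided by the SD of a single condition, which is the reading that gives the stated correlation and equal variances a purpose, and on 28 being the total number of children. No dropout or multiplicity adjustment is counted. Losses below 28 completers, or testing at a Holm-reduced α, would lower power further. The error is in a stated design property, and it is cheap to correct.

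**What to change.** Replace the concluding sentence of the Power section with one that follows from its inputs and names the basis of calculation. For example:

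> With 28 completers, a two-sided α of 0.05 and a correlation of 0.60, a paired t-test has about 81% power (84% by the normal approximation) for a standardized effect of 0.50; the effect detectable with 90% power is about 0.57 (0.55 by the normal approximation).

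The 0.90 power input earlier in the paragraph should be amended to agree. If the original calculation turns out to have been one-sided, the test should not simply be relabelled: that would change the standard of evidence and is a separate decision.

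The cost is an edit to one paragraph and a less favourable stated power. It needs no extra participants and no change to procedures or analysis.

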#### Data Analysis

Data will be analyzed using SAS software, version 9.4 (SAS Institute Inc., Cary, NC, USA). Data will be tested for normality using the Kolmogorov-Smirnov 'Goodness of Fit Test.' For normally distributed data, *t*-tests will be used to compare outcomes between noise cancelling headphones and sham headphone controls; for data that are not normally distributed, Wilcoxon's test will be used. We will also investigate for the effects of sequence on the outcomes. This will be accomplished using analysis of variance (RMANOVA) with a within factor of 'noise cancelling headphones on first study visit' vs. 'noise cancelling headphones on second study visit.' Because of the use of multiple tests on the same set of data, alpha adjustment will be conducted in accordance with the Bonferroni-Holm procedure. We will also calculate Cohen's d values for all outcomes as an estimate for relevant effect size estimates for future studies. Missing data will be managed using standard multiple imputation procedures.

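### A normality test on an unnamed quantity chooses each outcome's test, and the device comparison as written has no period term; one prespecified period-adjusted crossover analysis would settle both

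*Combined protocol and SAP*

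**What the plan says.** The Data Analysis section sets a two-stage rule. First, "Data will be tested for normality using the Kolmogorov-Smirnov" test. Outcomes judged normal get a t-test of noise cancelling against sham; otherwise "for data that are not normally distributed, Wilcoxon's test will be used". The section does not state:

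- which quantity is checked (scores, change from baseline, within-child differences or residuals);
- the significance level of the check;
- whether the t-test is paired or two-sample, or whether the Wilcoxon test is signed-rank or rank-sum.

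The same section adds a repeated-measures ANOVA comparing children who wore the active device first with those who wore it second, a Holm correction, and Cohen's d for all outcomes. The ANOVA is not linked to the device comparison, and it labels order a within factor although each child has only one order.

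The Power section assumes "no period effect, equal carryover effects between the two sequences". The Study Table of Assessments schedules the CANTAB and the academic tasks at Visits 2, 3 and 4. The Study Design overview says that the order of sessions is randomized and balanced.

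**The concern.** In a two-period crossover the device effect is carried by the within-child difference. Scores from children aged 6 to 18 may well be skewed between children while the differences are close to normal. Two analysts who both follow the section faithfully could check different quantities and so run different tests. Outcomes in one Holm family could then have mean-based or rank-based p-values, and a mean-based Cohen's d could sit beside a rank-based p-value.

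Separately, the same tasks are repeated across visits, so a shift between Visits 3 and 4 is plausible. A paired t-test or signed-rank test leaves that shift in the error term. At stake is power for the main comparison in a study with about 28 pairs.

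**Working it through.** **Inputs from the Power section.** Two-sided test ("Sample size calculations assumed a 2-tailed statistical test of size" 0.05), power 0.90, "effect size estimate of 0.50", and "a correlation between groups of 0.60, and equal variances between groups". The stated result is "a sample size of 28 will allow us to detect" that effect; the recruitment section plans 30 children.

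**The plan's own figure.** In SD units the paired difference has variance 2(1 − 0.60) = 0.80, so SD 0.894. Then n = (1.960 + 1.282)² × 0.80 / 0.50² = 10.51 × 3.2 = 33.6, i.e. 34 (36 with the paired t). The stated 28 does not reproduce. That is a separate matter; here it means only that the reference power at n = 28 is 0.81 (paired t), not 0.90.

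**Assumptions that are not in the documents.** The period shift, the shape of any skewness, and a 5% level for the normality check with a critical value allowing for estimated mean and SD.

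**Step 1: does the quantity checked matter?** Simulations with n = 28 and correlation 0.60. Entries are the share of trials in which normality is rejected, so that Wilcoxon is chosen.

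| Assumed data | Check on scores | Check on change from baseline | Check on differences |
|---|---|---|---|
| Skewed between children, normal differences | 22–32% | about 10% | about 4% |
| Both parts moderately skewed (gamma, shape 2) | 41–42% | 21% | 13% |
| Skewed within-child errors (lognormal) | 28% | not run | 68% |

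The 10% is also the rate for fully normal data when changes from baseline are checked, because two checks are run, one per condition. Checks on scores and on differences lead to different tests in 43% of trials in the second row and 51% in the third.

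**Step 2: does the gate do harm in itself?** With no period effect, type I error of the two-stage rule was 0.040 to 0.053 in every scenario run. Its power was within about 1 point of the plain paired t-test when differences were normal, and 1 to 5 points higher when they were skewed. No inflation and no power loss was found.

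**Step 3: what does omitting period cost?** Let π be the shift from Visit 3 to Visit 4 in SD units. The difference, noise cancelling minus sham, is moved by −π in one sequence and +π in the other. With equal sequences these cancel in the mean, so the device estimate is unbiased. The spread that the paired test sees becomes about √(0.80 + π²).

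| π (assumed) | SD of difference | Power, unadjusted, approximate formula | Power, unadjusted, simulated | Power, period-adjusted |
|---|---|---|---|---|
| 0 | 0.894 | 0.81 | 0.82 | 0.81 |
| 0.2 | 0.917 | 0.79 | 0.80 | 0.81 |
| 0.3 | 0.943 | 0.77 | 0.78 | 0.81 |
| 0.5 | 1.025 | 0.70 | 0.72 | 0.81 |
| 0.8 | 1.200 | 0.57 | 0.58 | 0.81 |

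The formula is slightly pessimistic because it treats the shift as random noise, whereas balance removes it from the mean. The adjusted test is a two-sample t on period differences by sequence (26 df); with no shift it has power 0.813 against 0.814 for the paired t (27 df). Under the null, type I error of the unadjusted test falls to about 0.025 at π = 0.5 and 0.010 at π = 0.8.

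**The case against.** The strongest reply has four parts.

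1. *The gate causes no demonstrated harm.* This stands. Type I error stays near 5%, and for skewed differences the gate gains a little power. The rule is also written down in advance. What is missing is the variable, the level and the form of each test.
2. *All the quantified loss comes from assumed period shifts.* This stands as a limit on size. The Power section assumes none, and every child does the full battery at baseline, so first-exposure practice comes before both experimental sessions. At 0.2 or 0.3 SD the loss is only 1 to 3 points.
3. *The plan does look at order.* It does, in the separate ANOVA, but that analysis does not alter the device test.
4. *The study is a pilot.* True, and it limits the weight of the point, not the value of a change that costs only wording.

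Two stronger readings are tempting. A reader might infer that normality is checked on the wrong quantity. The section says only that data are tested, and the synopsis objectives refer to change from baseline, a reading that removes most of the effect of between-child skewness. The quantity is unspecified, not shown to be wrong. A reader might also infer that neither test could ever adjust for period. A two-sample t-test or a rank-sum test on period differences by sequence does adjust, and the section does not exclude either. What can be said is that no adjustment is stated.

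**Conclusion.** The point holds as a low-cost improvement. The section leaves the test for each outcome to a normality check on an unnamed quantity, and states no period term in the device comparison. The choice of test can turn on which quantity the analyst checks. Omitting period costs about 1, 3, 9 and 23 points of power at assumed shifts of 0.2, 0.3, 0.5 and 0.8 SD (0.81 less 0.80, 0.78, 0.72 and 0.58), and nothing material at zero.

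These figures rest on 28 children split equally between sequences, effect size 0.50, correlation 0.60, normal data and an unadjusted two-sided 0.05. The documents give no estimate of the period shift.

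The documents do not support a claim of false-positive inflation: the gate leaves type I error near 5%, and an omitted period effect makes the test conservative. Nor do they support a claim of bias in the device estimate while order is balanced; that would need unequal sequence numbers, for example after dropout.

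**What to change.** Replace the normality gate with one prespecified analysis for every CANTAB and academic outcome: a linear mixed model with device, period and sequence as fixed effects and child as random effect. With complete data this is equivalent to a two-sample t-test on period differences by sequence, which could be named instead. State that the device p-value entering the Holm procedure comes from this model.

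Add a rank-sum test on period differences by sequence as a sensitivity analysis, reported for every outcome whatever the residuals look like. The separate sequence ANOVA is then no longer needed to address order.

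The cost is wording in the Data Analysis section; no visit, measurement or sample size changes. The downside is somewhat less power than a rank test if within-child differences are strongly skewed: about 82% against 88% in the most skewed scenario simulated, without a period effect. The sensitivity analysis would show this. If there is no period effect, adjustment costs one degree of freedom.

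### The device comparison has no period term, so a Visit 3-to-4 shift would cost power and, if sequences are unequal, slightly bias the estimate

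*Combined protocol and SAP*

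**What the plan says.** The Synopsis describes a two-sequence, two-session crossover: "The order of sessions will be randomized and balanced across participants". At Visits 3 and 4, "Participants will complete the CANTAB ADHD battery with either noise cancelling headphones or" the sham, and the academic tasks follow the same scheme. The Table of Assessments shows that both sets of tasks are also given at Visit 2.

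Under Data Analysis, t-tests are planned for normally distributed data; these "tests will be used to compare outcomes between noise cancelling headphones and sham headphone controls". Wilcoxon's test is used otherwise. The text does not say that the tests are paired and names no period or visit term. It then adds: "We will also investigate for the effects of sequence on the outcomes". This is to be an RMANOVA with headphones first versus second as a factor. The model is not written out, and nothing says that it supplies or adjusts the device estimate. On missing data: "Missing data will be managed using standard multiple imputation procedures".

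The Power section assumes "no period effect, equal carryover effects between the two sequences".

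**The concern.** Children repeat the same tasks a week or so apart, so a change between Visits 3 and 4 (practice, fatigue, loss of interest) is possible whichever device is worn. The plan assumes there is none and uses a device test that cannot remove one.

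Only a shift between Visits 3 and 4 matters. Each child has a single baseline, which cancels in the within-child difference. Practice gained from Visit 2 to Visit 3 is present in both sessions and cancels too.

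Two things are at stake. The first is power in a study of 30 children. The second is the Cohen's d values, which are planned as estimates for future studies. A shift left in the SD of the differences lowers a paired d, and unequal sequences move the estimate itself up or down.

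**Working it through.** **Inputs from the Power section.** Effect 0.50 (taken as the mean difference over the single-condition SD), correlation 0.60, equal variances, two-sided alpha 0.05, n = 28. **From Recruitment & Randomization:** 30 recruited. **Assumed:** a paired test; 1:1 sequences; Visit 3-to-4 shifts π of 0.1 to 0.5 SD.

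**The plan's own figure.** The variance of the within-child difference is 2(1 − 0.60) = 0.8, so its SD is 0.894 and the paired effect is 0.50/0.894 = 0.559. For two-sided 0.05 and 90% power, the normal formula gives n = ((1.960 + 1.282)/0.559)² ≈ 33.6, that is 34; the t-test needs 36. The stated 28 is not reproduced. At n = 28 power is 84.1% (normal) or 81.4% (t). That is a separate and larger issue. Here it means only that the losses below start from about 81%, not 90%.

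**How the shift enters.** Let Visit 4 scores be better by π. The noise-cancelling minus sham difference then has mean 0.50 − π when noise cancelling comes first and 0.50 + π when sham comes first.

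- Expected sample variance of all differences at 14/14: 0.8 + π² × 28/27.
- Mean of all differences: 0.50 + π(n_sham-first − n_NC-first)/N.

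The period-adjusted estimate averages the two sequence means, so π cancels. Its variance is pooled within sequence, on N − 2 degrees of freedom.

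**Power at 14/14** (simulation, 200,000 trials per setting; a repeat with 400,000 trials at 0.2, 0.3 and 0.5 SD agreed closely):

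| Shift (SD) | Variance ratio | Unadjusted power | Adjusted power | Loss (points) | Unadjusted type I error |
|---|---|---|---|---|---|
| 0.1 | 1.01 | 81.1% | 81.4% | 0.3 | 4.9% |
| 0.2 | 1.05 | 80.0% | 81.3% | 1.3 | 4.4% |
| 0.3 | 1.12 | 78.3% | 81.4% | 3.1 | 3.9% |
| 0.5 | 1.32 | 72.2% | 81.2% | 9.0 | 2.5% |

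The adjusted test's type I error stays at 4.9% to 5.0%.

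**If all 30 complete (15/15):** 82.9% vs 84.1% at 0.2 SD, 81.2% vs 84.0% at 0.3 and 75.7% vs 84.2% at 0.5.

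**Wilcoxon signed-rank (normal approximation, 14/14):** 79.0% with no shift, 77.3% at 0.2 SD and 68.6% at 0.5 SD, so switching to ranks does not help.

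**Unequal completers.** If two of 30 drop out from 15/15, the most unequal split is 15/13. The bias is π × 2/28: 0.014, 0.021 and 0.036 SD at 0.2, 0.3 and 0.5. Its direction depends on which sequence is larger (Visit 4 better; simulated means):

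| Shift (SD) | NC-first larger: estimate, power unadjusted vs adjusted | Sham-first larger: estimate, power unadjusted vs adjusted |
|---|---|---|
| 0.2 | 0.486, 77.8% vs 81.2% | 0.514, 82.2% vs 81.1% |
| 0.3 | 0.479, 74.6% vs 81.1% | 0.521, 81.5% vs 81.0% |
| 0.5 | 0.463, 64.9% vs 80.9% | 0.535, 78.5% vs 81.0% |

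**Cohen's d at 14/14.** A paired d of 0.559 falls to 0.50/√0.893 = 0.53 at 0.3 SD and 0.50/√1.059 = 0.49 at 0.5 SD, with no change in the true device effect.

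**Sensitivity** (loss for shifts of 0.2 to 0.5 SD at 14/14): 1.2 to 8.2 points at correlation 0.70, 1.1 to 7.7 at 0.40, 0.8 to 5.4 if one-sided, and 2.1 to 13.6 at a Holm first step of 0.05/3 (three tests assumed; the plan gives no number).

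**Price of adjusting when there is no shift** (noncentral t, n = 28): 81.4% on 27 degrees of freedom, 81.3% on 26.

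**The case against.** The strongest reply is that the effect is small and hypothetical. The documents give no period effect. Every child has already done the tasks once at Visit 2, and nothing in the documents points to a further change as large as half an SD between Visits 3 and 4. At 0.1 SD the loss is only 0.3 point. This stands: 0.5 SD should be read as an upper scenario.

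With balanced sequences the plain test is valid, and if anything conservative. This also stands, but balance does not remove the variance inflation.

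The bias needs both a shift and unequal sequences, and imputing all 30 children could restore 15/15. That is possible, but the imputation model is not specified, and restoring balance would not remove the variance inflation. With unequal sequences the unadjusted test can even have more power, as the second table shows, so the loss is not universal.

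The effect on Cohen's d depends on its definition, which the plan does not give. If d uses the single-condition SD, a balanced 0.5 SD shift lowers it only from 0.500 to 0.485.

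Finally, the RMANOVA partly addresses order. With device as a factor, its device-by-sequence term would be the period effect. But it is presented as an additional investigation, and it calls order a within factor although each child has only one order. The device test therefore remains unadjusted as written.

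**Conclusion.** The concern holds, as a modest efficiency point. Nothing in the plan adjusts the device estimate for a shift between Visits 3 and 4. The loss at 14/14 is about 1 to 3 points for shifts of 0.2 to 0.3 SD, rises to 9 at 0.5 SD and is negligible at 0.1 SD. Bias is zero with equal sequences and at most 0.036 SD at 15/13 for shifts up to 0.5 SD.

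These figures rest on assumed shifts, a paired test, the plan's effect and correlation, and two-sided alpha 0.05 before any Holm step. If the t-test were unpaired, power at n = 28 would be about 43% before any shift, so the pairing needs to be stated in any case.

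**What to change.** Make the primary device test period-adjusted:

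- Fit a mixed model with treatment, period and sequence as fixed effects and child as a random effect. For complete data, the equivalent is a two-sample t-test comparing Visit 3 minus Visit 4 differences between the sequence groups; half the difference in means is the device effect.
- If the data are not normal, use a Wilcoxon rank-sum test on those same differences.
- State that the device estimate and p-value come from this analysis and not from a separate RMANOVA.
- Include sequence and period in the imputation model.
- Say which SD standardizes Cohen's d; if it is a paired d, use the within-sequence SD of the differences.

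The adjusted test no longer needs the no-period-effect assumption. It still needs the equal-carryover assumption that the plan already makes. The cost is SAP wording and one degree of freedom, about 0.1 point of power if there is no shift. The randomized sequences already supply the data.
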